### Overview

The overarching goal of this project is to characterize the influence of dopaminergic system dysfunction on the clinical presentation of late-life depression (LLD) across multiple Research Domain Criteria (RDoC) domains (Positive Valence Systems, Cognitive Systems, and Sensorimotor Systems) at several levels of analysis (cellular [PET], structure / circuit [MRI], and functional / self-report). This IRB pertains to procedures completed at Columbia/NYSPI. A companion grant in this Collaborative R01 project takes place at Vanderbilt University Medical Center and utilizes similar, but not identical procedures (e.g., the PET scanning at Vanderbilt utilizes a different radiotracer). Thus, we have opted to have separate IRB protocols for this project. At Columbia/NYSPI we will enroll 60 elderly depressed outpatients who exhibit behavioral evidence of dopaminergic dysfunction, defined as either slowed processing speed or slowed gait speed. To disentangle the effects of depression from age-related changes, 30 psychiatrically healthy elders also will complete baseline evaluation. After determination of eligibility, baseline assessments include PET imaging measurements of dopamine synthesis and receptor density, neuromelanin-sensitive MRI measurement of long-term nigrostriatal dopamine transmission, task positive MRI focused on effort-based decision making and reward processing, and a comprehensive psychiatric, neurocognitive, and physical performance evaluation. To examine responsivity of the dopamine system to dopamine supplementation with L-DOPA, the 60 depressed subjects (ONLY) then will be randomized to L-DOPA or placebo for 3 weeks, followed by repeat multimodal MRI, neurocognitive and behavioral assessments. In a cross-over design, participants will then receive the opposite intervention for an additional 3 weeks followed by clinical and cognitive assessments only.

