**7. Otherwise eligible subjects who are currently taking an ineffective antidepressant medication (i.e., the individual is symptomatic at a level meeting inclusion criteria) will be offered participation as above after a discussion of the risks, benefits, and alternatives. No patients will be taken off of effective antidepressant medications solely for the purpose of research. Should an individual taking an ineffective antidepressant medication wish to participate and sign consent, their psychiatric care will be taken over by a CAAM study clinician after a discussion with their prescribing physician. Such participants will be tapered off of the ineffective medication as per standard clinical practice (depending on the medication) and be followed closely in CAAM, likely through weekly visits. Should a participant be unable to tolerate the medication taper due to increasing depressive symptoms, they will be withdrawn from the study and entered into the 3 month open treatment period directly. Once participants are washed off of the medication they will proceed with the study assessment described in points 8-10 immediately below. Subjects must be off medication for 2 weeks prior to neuroimaging procedures and beginning the L-DOPA study medication.**

**8. Other neuropsychological measures completed at baseline include trained study rater (BA, RN, SW) assessment of processing speed using the Pattern and Letter Comparison Tests, broad cognitive evaluation with the NIH Toolbox, and evaluation of executive function via the NIH-EXAMINER battery designed to assess executive functions reliably, comprehensively, and efficiently (154-155). This battery examines working memory, inhibition, set shifting, fluency, insight, planning, social cognition and behavior. We also include the supplemental NIH Toolbox Auditory Verbal Learning (Rey) Test for a robust assessment of episodic memory and allow for classification of amnestic mild cognitive impairment.**

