### **Clinical treatment**

23. For the mechanistic probe of dopaminergic functioning using LDOPA, a crossover trial will be conducted. In Step 1, participants will be randomized to initially receive either active L-DOPA or matching placebo based on a block design using R Statistical Software version 3.4.3 (R Foundation for Statistical Computing, Vienna, Austria). Participants, physicians and research staff will be blinded to group assignment. The NYSPI Pharmacy will maintain the randomization key for each site and can unblind individual subjects in emergencies. The blind will not be broken until study completion. Following Step 1, participants will have repeat MRI scanning and cognitive/behavioral testing, then undergo a 1 week taper and wash out period before being crossed over to the opposite treatment (Step 2). Repeat cognitive and behavioral testing will occur after Step 2 but there will be no further neuroimaging.

24. Subjects will take active or placebo tablets three times daily (9am, 1pm, 5pm). Those assigned to L-DOPA will begin with a Week 1 L-DOPA daily dosage of 150mg, or 1.5 25mg carbidopa/100mg levodopa

---

tablets at 9am and placebo tablets at 1pm and 5pm. In Week 2 the L-DOPA daily dose will increase to 300mg (1.5 25mg carbidopa/100mg levodopa tablets at 9am and 5pm, with placebo at 1pm), followed by a Week 3 L-DOPA daily dose of 450mg (1.5 25mg carbidopa/100mg levodopa tablets three times daily). Subjects assigned to placebo will take 1.5 placebo tablets three times daily for three weeks. Individuals will be instructed to maintain the same timing of doses throughout the study. Individuals unable to tolerate an increased dose will have their dosage reduced to the maximum previously tolerated dose.

25. Following the three-week Step 1 Phase, there will be a one-week taper period. Subjects will be instructed to decrease their dosage to 1.5 tablets twice daily for 3 days, followed by 1.5 tablets once daily for three days, then discontinue tablets. Subjects will then restart an identical dosing regimen while being crossed over to the opposite treatment assignment for Step 2.

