26. At each weekly visit, subjects will meet with a psychiatrist or study physician. Both in our Pilot study and the literature overall, L-DOPA is an extremely well tolerated medication at doses < 600mg, which is substantially less than the doses often reached in the treatment of Parkinson's disease (900-1200mg). L-DOPA has been administered to healthy subjects in single dose studies and found to be well-tolerated. In Parkinson's disease, a recent clinical trial published in the New England Journal of Medicine randomized patients to receive 150mg, 300mg, or 600mg L-DOPA for 40 weeks. No dyskinetic effects or other neuropsychiatric effects were observed that were greater than the placebo group.

27. Participants will be given the option to receive medication reminders via text messages three times daily (morning 9am, midday 12pm, evening 5pm) adhering to the study medication schedule. Text messages will be automatically sent out by service provider [www.remindercall.com](http://www.remindercall.com). Participants will be able to opt-in and opt-out of this service at any time during the study by either replying "STOP" to any text message or by contacting the study coordinator.

26. At the conclusion of Step 2, participants will undergo another 1 week washout phase and then enter post-protocol open treatment, which will be offered for 3 months. Appropriate medication treatment options for depression will be discussed with each participant, which may include continued off-label use of LDOPA as discussed below.

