## Assessments

29. Subjects are expected to have a screening/evaluation visit, pre-treatment PET/MRI scanning day(s), and weekly visits during Steps 1 and 2 of the crossover trial (i.e., Weeks 0-3 [Step 1], 4 [taper], 5-8 [Step 2], 9 [taper]). At each clinic visit, depression severity measured using the MADRS and adverse events assessed. The presence of any suicidal thoughts will be assessed at every contact. Vital signs (weight, heart rate, blood pressure) will also be measured.

30. Cognitive assessments will be performed at baseline and after each step of the crossover trial. To obtain a broad assessment of cognitive function, we will administer the NIH Toolbox Cognition Battery that measures 6 ability subdomains and assess episodic memory functioning supplemental NIH Toolbox Auditory Verbal Learning (Rey) Test. Our primary outcome is processing speed, assessed using Coding from the Wechsler Adult Intelligence Scale-IV (WAIS-IV) and the Pattern and Letter Comparison tests (secondary outcomes). To assess executive function, we will supplement the NIH Toolbox with the NIH-

---

EXAMINER battery, which measures working memory, inhibition, set shifting, fluency, insight, planning, social cognition and behavior (secondary outcomes).

31. Gait will be assessed at baseline and after each step of the crossover trial as both a single and dual tasks (ST, DT) using the GaitRite system (Sparta, NJ), which assesses gait parameters in real time (gait speed, cadence, stride length). For the ST (primary gait outcome), participants are instructed to walk at their usual or normal speed over the 15' walking course. For the DT (secondary outcome), participants are instructed to walk at their usual pace while simultaneously verbally listing as many animals as possible (fluency DT). In addition, a counting DT will be used in which participants are instructed to walk at their usual pace while simultaneously performing serial subtractions by threes starting at 100.

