### End of study procedures

33. Following the 8 week (in total) duration crossover study, endpoint assessments of psychiatric symptoms, cognition, and motor functioning will be made. Once post-treatment research procedures are completed, patients will enter 3 month open treatment period provided free of charge as described below.

You can upload charts or diagrams if any

Figures.pdf

Dosimetry chart for [18F]DOPA.pdf

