## Research Related Delay to Treatment

Will research procedures result in a delay to treatment?

Yes

Maximum duration of delay to any treatment

None.

Maximum duration of delay to standard care or treatment of known efficacy

Since patients will be assigned to placebo for one phase of the crossover study and the effects of L-DOPA on depression in this population are currently unknown, there will be an 8-week duration delay to receiving an agent of known efficacy to treat depression posed by subjects' participation in this study.

Treatment to be provided at the end of the study

We will provide 3 months of additional free clinic visits following the end of this project. At the conclusion of the 3 week study, a non-study clinician in our research clinic will be given the data on the subject's response to L-DOPA. This clinician will discuss with each subject on a case-by-case basis the risks and benefits of continuing L-DOPA treatment as well as other treatment options if warranted. Those who have benefited from the treatment and have not had significant side effects may elect to continue receiving L-DOPA after receiving an explanation of the potential risks of chronic administration. If they do not want to continue L-DOPA, it will be discontinued after a 3 day step-down withdrawal of the drug. Transferring after-study care to a non-study clinician protects against the development of bias in the study clinicians and offers optimal clinical care to the subjects at the study conclusion.

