**3. Delay in Antidepressant Treatment Initiation:** As specified in the above selection criteria, participants in this study will have a DSM 5 depressive disorder and MADRS  $\geq 15$ , but current treatment with antidepressant medication is an exclusion criterion. Otherwise eligible subjects who are currently taking an ineffective antidepressant medication (i.e., the individual is symptomatic at a level meeting inclusion criteria) will be offered participation after a discussion of the risks, benefits, and alternatives. Those wishing to participate will undergo a medication washout following standard clinical practice and be closely followed by study clinicians until they are eligible to begin the study. The maximum duration of delay of treatment for depression with an agent of known efficacy will be 8 weeks. No patients will be taken off of effective antidepressant medications solely for the purpose of research, and patients will be withdrawn from the study and treated if clinically indicated and desired by the patient.

A number of precautions have been taken to safely maintain participants antidepressant-free for the duration of the proposed study. First, our selection criteria exclude individuals who are judged to be at high risk of suicide (MADRS suicide item  $> 4$ ). Second, we have stringent criteria for early discontinuation and initiation of appropriate open clinical treatment. These criteria are (1) participant withdraws his or her consent; (2) significant clinical worsening in the judgment of the study clinician; (3) a CGI-Improvement rating of 6 (worse) or 7 (much worse) for 2 consecutive visits, or (4) development of significant side effects or an adverse event. Any subjects meeting any of these criteria will be withdrawn from the study and treated as clinically indicated. Furthermore, subjects may be withdrawn if they repeatedly miss scheduled appointments or clinical worsening necessitates more intensive treatment. Finally, following the study,

---

subjects are offered state-of-the-art clinical visits at no cost to them or their insurer for 3 months, although they will be responsible for the cost of any antidepressant medications.

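### The stated 8-week maximum delay to effective depression treatment leaves out the antidepressant taper and 2-week drug-free period, and does not match the visit schedule, which runs to Week 9

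*Protocol*

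**What the plan says.** The maximum delay is given twice in the protocol. Item 3 of Risks/Discomforts/Inconveniences states: "The maximum duration of delay of treatment for depression with an agent of known efficacy will be 8 weeks". Research Related Delay to Treatment states that "there will be an 8-week duration delay to receiving an agent of known efficacy to treat depression".

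The crossover periods are set out elsewhere:

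- Step 1 and first taper (Clinical treatment, item 25): "Following the three-week Step 1 Phase, there will be a one-week taper period".
- Step 2 (Overview): "participants will then receive the opposite intervention for an additional 3 weeks".
- After Step 2 (last item of Clinical treatment): "participants will undergo another 1 week washout phase and then enter post-protocol open treatment".
- Total (End of study procedures, item 33): "Following the 8 week (in total) duration crossover study".

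Point 7 of Evaluation adds a stage before Step 1 for some participants. Those on an ineffective antidepressant who sign consent are tapered off it, over a time that depends on the drug and is not stated. Then "Subjects must be off medication for 2 weeks prior to neuroimaging procedures and beginning the L-DOPA study medication".

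Item 29 of Assessments places the visits at "Weeks 0-3 [Step 1], 4 [taper], 5-8 [Step 2], 9 [taper]". Point 2 of Evaluation describes participation as lasting 6-8 weeks.

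**The concern.** A stated maximum has to cover everyone it applies to. Item 3 of the risk section covers participants who are washed out of an antidepressant, and describes their washout immediately before giving 8 weeks. If 8 weeks is only the length of the crossover, the figure is too low for the participants who stop a drug in order to enter.

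At stake is the accuracy of a risk figure submitted to the IRB. It concerns symptomatic depressed patients aged 60 or older who forgo standard treatment while in the study. No endpoint, estimand or power calculation is affected. The Week 9 visit label raises a second question: whether the crossover itself lasts 8 weeks or 9.

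**Working it through.** **Inputs, all from the protocol**

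| Period | Length | Where |
|---|---|---|
| Step 1 | 3 weeks | Clinical treatment, item 25 |
| Taper after Step 1 | 1 week | Clinical treatment, item 25 |
| Step 2 | 3 weeks | Overview |
| Washout after Step 2 | 1 week | Clinical treatment, last item |
| Drug-free period before imaging and study drug | 2 weeks | Evaluation, point 7 |
| Antidepressant taper before that | not stated | Evaluation, point 7 |
| Visit schedule | Week 0 to Week 9 | Assessments, item 29 |

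**Step 1. Reproduce the stated figure.** 3 + 1 + 3 + 1 = 8 weeks. This equals the stated maximum and the total in End of study procedures. The crossover uses all 8 weeks, so nothing is left for any period before Step 1.

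**Step 2. Add the required drug-free period.** 8 + 2 = 10 weeks for a participant washed out of an antidepressant. 10/8 = 1.25, so the stated maximum is exceeded by 2 weeks (25%).

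**Step 3. Try the most favourable counting.** Set the antidepressant taper to zero.

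- Final washout week left out: (3 + 1 + 3) + 2 = 7 + 2 = 9 weeks.
- Final washout week replaced by the 3-day step-down mentioned in Research Related Delay to Treatment: 9 weeks and 3 days.

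Both exceed 8 weeks.

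**Step 4. Allow for the taper.** Its length is not given. Assuming 1 to 4 weeks, for illustration only, the total is 10 + 1 = 11 to 10 + 4 = 14 weeks. Time to schedule the baseline scans is extra; item 11 of MRI Scanning expects MRI and PET to fall on different days in most cases.

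**Step 5. Check the visit schedule.** Week 0 to Week 9 is 9 elapsed weeks. The extra week lies between the steps: Step 1 ends at Week 3 and Step 2 begins at Week 5, a gap of 2 weeks against a 1-week taper. On these labels the delay is 9 weeks without antidepressant washout and 9 + 2 = 11 weeks with it, or 12 to 15 weeks with the same assumed taper of 1 to 4 weeks.

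| Participant | Stated | From period lengths | From visit labels |
|---|---|---|---|
| Already drug-free | 8 | 8 | 9 |
| Washed out, taper set to zero | 8 | 10 | 11 |
| Washed out, assumed taper of 1-4 weeks | 8 | 11-14 | 12-15 |

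**The case against.** The best defence is that 8 weeks is a correct sum with a narrower meaning. Research Related Delay to Treatment ties the figure to the crossover, and the risk section describes the washout as coming before participants are eligible to begin the study. If the clock starts at the first dose of study drug, 8 weeks is right. However, point 7 of Evaluation puts consent before the antidepressant taper. The drug-free period is an entry requirement of the research, and the study clinic takes over care during it. That time is delay caused by the research, and a figure called a maximum should include it.

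Other points carry some weight:

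- **The taper.** During it the participant still takes a drug, though one described as ineffective, so whether it counts as delay is a matter of definition. The 2 drug-free weeks exceed the maximum without it.
- **The visit labels.** Each step has four labels (0-3 and 5-8), so Week 5 may be meant as a Step 2 baseline rather than an extra elapsed week. The 9- and 11-week figures therefore depend on a literal reading.
- **The 6-8 weeks in Evaluation.** Its upper end is 8, so this is only a minor inconsistency.
- **The exit from the study.** The 3-day step-down differs from the final washout week. It changes the size of the excess but does not remove it.
- **Safeguards.** Close follow-up, withdrawal to open treatment if the taper is not tolerated, and the rule against stopping an effective drug solely for research all reduce the risk. They do not shorten the delay for someone who completes the study.

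**Conclusion.** The concern holds. The 8-week maximum equals the crossover alone. For participants washed out of an antidepressant, the protocol's own periods give at least 10 weeks, which is 2 weeks (25%) above the stated maximum, before the taper and scan scheduling. This rests on counting the 2-week drug-free period as research-related delay and on the final washout week in Clinical treatment. Without that final week the total is still 9.

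The conflict with the visit schedule is real but secondary: its labels span 9 weeks where the period lengths give 8, and the 11-week figure depends on those labels. For participants already drug-free, 8 weeks agrees with the period lengths. The documents do not say how many participants would need washout, so the number affected is unknown.

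**What to change.** Reconcile Evaluation (points 2 and 7), Clinical treatment, Assessments (item 29), End of study procedures, Research Related Delay to Treatment and item 3 of the risk section to a single schedule. Say what the Week 5 and Week 9 labels mean, and which account of the exit from Step 2 applies when the delay is counted.

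Then define when the delay starts and ends, and state its maximum separately for two groups: participants entering without antidepressant washout and those entering with it. The second figure should count the taper (as a range if it varies by drug), the 2-week drug-free period, time for baseline imaging, both steps and both tapers. The consent form was not available for this review; check that it carries the same figures.

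The cost is protocol wording, and consent wording if the check shows it is needed, together with a less favourable stated delay. No change to the schedule or to clinical management is proposed.

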## **Methods to Protect Confidentiality**

Describe methods to protect confidentiality

All records of the participating subjects will be kept in a locked room with access provided only to staff members. Patients' names will be linked with code numbers in a password protected file to which only the research assistant has access. Only these code numbers will appear on all pill bottles and paper measures collected during study. All data collected will be kept confidential and used for professional purposes only. Publications using these data will be done in a manner that protects the subjects' anonymity. All electronically stored data will be accessible by password known only to the principal investigator and research assistants for the study.

The data obtained for this study and biospecimens could be used for future research studies or may be distributed to another investigator for future research studies, however all information **including biospecimens** will be de-identified **and will not include whole genome sequencing (i.e., sequencing of a human germline or somatic specimen with the intent to generate the genome or exome sequence of that specimen)**. Biospecimens will not be used for commercial profit. Clinically relevant research results, including individual research results may be available to participants at their request but such request will be granted under the discretion of the study doctor. Participants may be contacted in the future by the study team for future studies.

Data shared with the National Institute of Mental Health Data Archive (NDA) will maintain patient confidentiality by ensuring exclusion of all 18 identifiers (outlined by HIPAA) prior to data sharing.

*Will the study be conducted under a certificate of confidentiality?*

Yes, we have already received a Certificate of Confidentiality

## Direct Benefits to Subjects

### Direct Benefits to Subjects

There is no direct benefit to subjects. If L-DOPA treatment is effective in ameliorating slowing, subjects may experience improved quality of life and decreased of falls and other sequelae of slowing.

## Compensation and/or Reimbursement

Will compensation or reimbursement for expenses be offered to subjects?

Yes

Please describe and indicate total amount and schedule of payment(s).

Include justification for compensation amounts and indicate if there are bonus payments.

All subjects who complete a screening visit will be reimbursed \$35.

Eligible depressed subjects (N=60), will be reimbursed \$150 for cognitive/motor assessment sessions, **paid cash at the end of each visit**.

\$100 per MRI (2 MRI scan), and \$200 per [18F]-FDOPA PET scan. This equates to \$585 per depressed participant. **This money will be paid in 1 lump sum payment at the end of the study. Payments typically require 1-3 weeks to process and will be mailed in the form of a check.**

Eligible Non-depressed control subjects (N=30) will be reimbursed \$50 for cognitive/motor assessment session, **paid cash at the end of each visit**.

\$100 for MRI (1 MRI), and \$200 for [18F]-FDOPA PET scan. This equates to \$385 per control participant. **This money will be paid in 1 lump sum payment at the end of the study. Payments typically require 1-3 weeks to process and will be mailed in the form of a check.**

